### 7.3. Reporting/Recording of AEs

Throughout the course of the study, all efforts will be made by the investigator to remain alert to possible AEs. The first concern will be the safety of the subject, and for providing

---

appropriate medical intervention. The period of observation for collection of AEs starts at index EP procedure until study exit. Any AE should be recorded on the appropriate study CRF.

## **7.4. Adverse Events Requiring Expedited Reporting**

### **7.4.1. Investigator Responsibilities**

The Investigator is responsible for reporting all SAEs, SADEs, and device deficiencies that could have led to a SADE to the EC, according to national regulations and EC requirements. The investigator will forward a copy of this report to the Sponsor and file it in the investigator site binder.

The Investigator will document all SAEs and SADEs, including device deficiencies in the study subject's file and report it to the Sponsor and to the Sponsor's (Designee) within 24 hours of knowledge of event. When medical reports (lab results, examinations, etc.) associated with AEs are submitted to the Sponsor or Sponsor's Designee, all personal subject information (name, address, etc.) *must* be removed or redacted. The redacted materials must be identified only with the subject ID number.

In the event of a subject's death, the Investigator will make reasonable effort to obtain a copy of the autopsy report and/or death summary. The Investigator will determine the cause of death and its relationship to the investigational device; the Investigator will record results on the AE case report form (CRF). The Investigator will include copies of an autopsy report, if available, and/or a death summary with this form.

### **7.4.2. Sponsor Responsibilities**

Upon notification of SAEs, the Sponsor will initiate and complete a review and evaluation of the event within time frames that will maintain reporting compliance with applicable regulatory agencies. The Sponsor is responsible for classification and reporting of AEs and ongoing safety evaluation of the clinical investigation in line with EN ISO 14155:2012 and regulatory requirements. If insufficient information is available to reach a definitive diagnosis, the Sponsor may instruct the CRA responsible for the site to contact the site to request additional confirmatory information, if any.

The Sponsor will ensure that its Designee will report all SAEs and device deficiencies that could have led to an SADE to the Competent Authorities in accordance with European Medical Devices Directive and all applicable national regulations including the medical device act of the Czech Republic and Denmark.

## **7.5. Anticipated Adverse Events Related to the CathVision Cube® System**

There are no anticipated Adverse Events specifically associated with the use of the CathVision Cube® System or similar CE-labelled EP recording devices currently available.

---

## 7.6. Anticipated EP-Procedure Adverse Events

Anticipated complications/AEs are defined as complications/events that can be reasonably associated with the EP catheter ablation procedures. The mitigations and treatments for these AEs will follow published guidance for the same AEs occurring with other commercially available devices [1].

Anticipated AEs include, but are not limited to:

- Air embolism
- Allergic reaction (including anaphylaxis)
- Anesthesia reaction
- Angina
- Aorto-right atrial fistula
- Arrhythmias, including exacerbation of pre-existing atrial fibrillation
- Arterial-venous fistula
- Cardiac perforation/ tamponade
- Cardiac thromboembolism
- Cardiac or respiratory arrest
- Catheter entrapment
- Cerebrovascular incident / Stroke
- Chest pain/discomfort
- Congestive heart failure
- Coronary artery dissection
- Coronary artery spasm
- Coronary artery thrombosis / occlusion
- Death
- Diaphragmatic paralysis
- Endocarditis
- Esophageal ulceration
- Gastroparesis
- Heart failure / pump failure
- Hemoptysis
- Hemoptysis
- Hemothorax
- Hypotension
- Hospitalization (initial and prolonged)
- Increased creatinine phosphokinase (CPK) level
- Infections
- Laceration
- Leakage of air or blood into the lungs or other organs due to perforation
- Left atrial esophageal fistula
- Major bleeding, requiring surgery or transfusion
- Myocardial infarction
- Obstruction or perforation or damage to the vascular system
- Pericarditis
- Pericardial effusion
- Phrenic nerve damage including Diaphragmatic paralysis

- 
- Pleural effusion
  - Pneumonia
  - Pneumothorax
  - Pulmonary edema
  - Pulmonary embolism
  - Pulmonary vein dissection
  - Pulmonary vein thrombus
  - Pulmonary hypertension
  - Respiratory depression
  - Skin burns
  - Severe PV stenosis or complete occlusion, even asymptomatic
  - Tamponade, potentially requiring surgery
  - Temperature elevation or fever
  - Transient Ischemic Attack (TIA)
  - Thromboembolism
  - Thrombosis
  - Unintended complete or incomplete AV, Sinus node, or other heart block or damage
  - Valve damage
  - Vascular bleeding / local hematomas / ecchymosis
  - Vasovagal reactions
  - Ventricular tachyarrhythmia
  - Volume overload

## 7.7. Device Deficiencies

**Device deficiency** is defined as an inadequacy of a medical device with respect to its identity, quality, durability, reliability, safety or performance.

Note, device deficiencies include malfunctions, use errors, and inadequate labelling. All device deficiencies or malfunctions that occur during the course of the study and could have led to an SAE must be reported, whether or not they were associated with an AE.

**Device malfunction:** failure of an investigational medical device to perform in accordance with its intended purpose when used in accordance with the instructions for use.

**User error:** act or omission of an act that results in a different medical device response than intended by the manufacturer or expected by the user.

The Device Deficiency CRF is specific for reporting all device deficiencies, or malfunctions that occur during the course of the study, whether or not they were associated with an adverse event. Device Deficiency CRFs should be submitted to the Sponsor within 24 hours of the occurrence defining the device deficiency.

Anticipated device deficiencies and malfunctions include but are not limited to:

- Catheter deflection deficiency or failure
- Malfunction of a catheter electrode

- 
- Malfunction of a catheter temperature sensor
  - Unexpected termination of ablation due to internal system error
  - Failure to initiate ablation due to internal system error
  - Temporary or sustained loss of catheter navigation/visualization capability/signal

Record any CathVision Cube® System deficiencies and malfunctions including but are not limited to:

- CathVision Cube® System issues (EPAMP/RecSW)
  - Not able to power on
  - Power indicators not on
  - Not able to connect to the standard of care EP system
  - Not able to retrieve signal from standard of care EP system
  - Not able to power down
  - Database issues
  - Backup data issues
  - Not possible to clear fault without reboot
  - CathVision Cube® System Recorder Software
    - Malfunction
    - Loss of power
    - Loss of wave form
  - Recording issues (interruption, stop)
    - Not able to create patient
    - Not able to save patient
    - Live Mode issues (not able to create/resume patient, etc.)
    - Review Mode issues (not able to retrieve a patient)
    - SW crashes
    - SW loses connection to EPAMP
    - Limitation: Only possible to review the latest recording file, while streaming is active
    - Bug: Not possible to use the notch filter, if high-pass and low-pass is set to 'None'
- Host Computer Malfunctions
  - Not able to boot/start
- User errors

---

## **8. Statistical Methods**

### **8.1. Sample Size Calculation**

This study is intended to demonstrate safety and performance of the device. As a result, no formal statistical hypothesis was applied to derive the sample size. A drop-out rate is expected to be low due to acute and low risk profile of CIP.

### **8.2. Descriptive Analyses**

Continuous variables will be summarized using standard quantitative statistics: number of non-missing observations, mean, standard deviation, median, quartiles and range (minimum and maximum observed values). The number of missing observations, if any, will also be summarized.

Categorical variables will be summarized using classical frequency statistics: number of non-missing observations and percentages by categories. Number and percent of missing data, if any, will also be summarized.

There are no predefined criteria for terminating the study based on statistical outcomes. Missing data will not be replaced or imputed.

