## 4. Clinical Investigation Plan (CIP)

### 4.1. Study Objectives

The primary objective is to evaluate the safety and technical performance of the of the CathVision Cube® System. Secondary objective is to benchmark the intracardiac electrogram signal quality compared to commercially available systems in subjects undergoing assessment and ablation of cardiac arrhythmias.

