### 4.2. Study Design

A prospective, multi-center, open-label, single arm study to evaluate the safety and technical performance of the CathVision Cube® System.

Subjects who are indicated to undergo EP procedure and meet all inclusion criteria will be enrolled in the study and undergo EP procedure using an approved EP system in conjunction with the CathVision Cube® System. Intracardiac signals will be passively recorded in parallel with the commercial (CE marked) EP recording system. The investigational device will not be used to direct clinical care decisions or therapy. The EP procedure will be guided by study site standards of care.

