## **5. Study Outcomes**

### **5.1. Primary Performance Outcome**

The Primary Performance Endpoint of the study will be evaluated as technical success of CathVision Cube® System to collect and record intracardiac signals during EP procedures with focus on:

- Recording low-voltage electrograms
- Logging time for arrhythmia termination / block
- Assessing the improved signal (baseline noise level peak-to-peak)
- Assessing compatibility of CathVision Cube® System with a commercially available 3D mapping systems Bioscience Webster Carto3 and GE Cardiolab. In addition, site standard of care available intracardiac catheters will be used.

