### **5.3.4. Visit 2: Index Procedure through Discharge**

During the index EP procedure, only procedures or steps from institutional standard of care / best practice will be used to treat the subjects.

When the subject is connected to the standard EP recording system, during manipulation of catheters or diagnostic tests, intracardiac signals will be recorded using the investigational device in parallel. It is not expected to cause any significant delays to the total procedure time as the final comparison of data recorded from Standard EP recording system and the tested device will happen post procedure.

Index EP procedure, the following will be documented

- EP data recording
- Change in cardiac medication
- Adverse events and device malfunctions
- Protocol deviations

Prior to discharge, the following will be documented:

- 12 lead ECG will be performed
- Change in cardiac medications
- Adverse events
- Protocol deviations

All subjects will exit the study after this visit.

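### Section 8.2 names no Cube-versus-commercial contrast and no unit of analysis, although the secondary objective is a benchmark against commercial systems recorded in parallel in the same subjects

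*Protocol*

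**What the plan says.** **The objective is comparative.** Protocol 4.1, like the synopsis, states: "Secondary objective is to benchmark the intracardiac electrogram signal quality compared to commercially available systems". One focus of the primary performance endpoint in 5.1 is also worded comparatively: "Assessing the improved signal (baseline noise level peak-to-peak". An improvement needs something to be improved upon.

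**The design supplies the comparator within each subject.** Section 4.2: "Intracardiac signals will be passively recorded in parallel with the commercial (CE marked) EP recording system". Section 5.3.4 adds that the "final comparison of data recorded from Standard EP recording system and the tested device will happen post procedure". It gives no measure, matching rule or unit for that comparison.

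**The stated analysis is univariate.** Section 8.1 says that "no formal statistical hypothesis was applied to derive the sample size". Section 8.2 then says: "Continuous variables will be summarized using standard quantitative statistics: number of non-missing observations, mean, standard deviation, median, quartiles and range". For categorical data it says: "Categorical variables will be summarized using classical frequency statistics: number of non-missing observations and percentages by categories". On gaps in the data: "Missing data will not be replaced or imputed". Section 8 has no other analysis content.

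**Related facts.** Up to 30 subjects are to be enrolled (synopsis and 4.4), and screen failures count towards that total (5.3.3). Section 1.3 gives different best-in-class noise levels for bipolar recordings (below 15 µV) and unipolar recordings (below 30 µV), and says improvement is sought particularly for unipolar recordings. Section 7.7 lists loss of waveform, interrupted recording and failure to retrieve a signal from the standard system among the malfunctions to be recorded.

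**The concern.** The protocol asks a comparative question, collects data suited to answering it, and then states an analysis that contains no comparison. Followed literally, 8.2 gives one noise table for the Cube and another for the commercial system. The reader is left to set two means and two SDs side by side.

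That loses the main strength of recording both systems in the same subject, which is that differences between subjects and procedures cancel within a pair. Two marginal tables do not show how consistently the Cube differs from its comparator, or how precisely the average difference is known.

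Leaving the unit open matters as well. Each subject can contribute many channels and time windows, and the protocol does not say at which level the comparison is made. In an open-label study whose device only the sponsor operates (9.5), the contrast and its unit are better fixed before the recordings are compared.

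**Working it through.** The protocol states no effect size, SD, margin, alpha or power, so there is no figure to reproduce. The check is what two separate summaries can and cannot deliver.

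**Inputs.** From the protocol: at most 30 subjects, two systems per subject, summaries limited to n, mean, SD, median, quartiles and range, and no imputation. Assumed for illustration, because the protocol gives no value: equal SDs (s) for the two systems, one value per subject per system, and a within-pair correlation r from 0 to 0.9.

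**Step 1: the mean difference.** Write C for a Cube value, S for the commercial value from the same subject, and D = C − S. If every subject has both values, mean(C) − mean(S) = mean(D), so the point estimate can be recovered. If some subjects lack one value, mean(C) and mean(S) are taken over different sets of subjects and their difference need not equal mean(D). The malfunctions listed in 7.7 make this foreseeable, and 8.2 does not say how incomplete pairs are handled.

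**Step 2: the spread of the difference.**

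Var(D) = s_C² + s_S² − 2·r·s_C·s_S

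With equal SDs this becomes SD(D) = s·√(2(1 − r)). The correlation r appears in neither marginal table, so SD(D) cannot be recovered from them.

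- r = 0: √2.0 = 1.41 s
- r = 0.5: √1.0 = 1.00 s
- r = 0.7: √0.6 = 0.77 s
- r = 0.9: √0.2 = 0.45 s

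**Step 3: the interval for the mean difference.** The 95% half-width is t(n−1)·SD(D)/√n when paired, and t(2n−2)·s·√(2/n) if the two tables are treated as independent samples. For example, with n = 30 and r = 0.5, it is 2.045 × 1.00/√30 = 0.373 s.

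| n | Treated as independent | Paired, r = 0 | Paired, r = 0.5 | Paired, r = 0.7 | Paired, r = 0.9 |
|---|---|---|---|---|---|
| 30 | 0.517 s | 0.528 s | 0.373 s | 0.289 s | 0.167 s |
| 20 | 0.640 s | 0.662 s | 0.468 s | 0.363 s | 0.209 s |

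The n = 20 row is an assumed case in which screen failures or unpaired recordings use up places. Pairing costs almost nothing at r = 0 (0.528 against 0.517) and at r = 0.9 cuts the half-width to about a third (0.167/0.517 = 0.32).

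**Step 4: the unit.** The phrase about non-missing observations is ordinary wording for n. Nothing else in section 8 says whether n counts subjects, channels or segments. The unit is therefore undefined.

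**The case against.** The strongest reply is that this is statistical analysis plan material. Pairing, averaging within subject, stratifying by recording type and choosing an interval are often left to that document, which may exist and is not shown. Section 8.2 says nothing false. It is generic enough to cover a per-subject difference if one were defined as a variable, and 5.3.4 does promise a comparison. The study is openly descriptive, so asking for a confidence interval is partly preference.

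Much of this stands. The absence of detailed method would not be a point in itself. What remains is that the protocol states its analysis, and that analysis does not name the quantity its own secondary objective asks for. Naming the contrast and its unit defines what is estimated and is more than programming detail. An interval for a mean difference is compatible with a descriptive study.

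A reader might infer more than the text supports:

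- **That 8.2 pools channels or segments as if they were subjects.** It does not say so; the unit is simply left open. Nor does it plan a standard error or interval, so there is no stated precision for clustering to overstate.
- **That it mixes bipolar and unipolar recordings.** Section 8.2 mentions neither, and 1.3 treats them separately. No shift in means from a differing channel mix can be attributed to the plan.
- **That every Cube signal has an exact commercial counterpart.** Parallel recording is stated; one-to-one matching of channels and segments is not.
- **That arrhythmia termination times should be compared between systems.** Section 5.1 lists logging that time as part of technical success, which can mean only whether the Cube logs it. The protocol describes no commercial time stamp and no synchronised clocks.

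**Conclusion.** The point holds in a limited form. Section 8.2 offers only one-variable summaries and names neither a Cube-versus-commercial contrast nor a unit of analysis, while 4.1, 4.2 and 5.3.4 set up a same-subject comparison.

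It would go too far to say that the comparison cannot be made at all. With complete pairs, the mean difference follows from the two means. What separate summaries cannot supply is the SD of the difference and an interval for its mean, and with incomplete pairs even the point estimate is no longer assured.

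The size can only be illustrated. With equal SDs and an assumed correlation of 0 to 0.9, the SD of the difference runs from 1.41 to 0.45 times the single-system SD. At 30 paired subjects the 95% half-width runs from 0.528 to 0.167 single-system SDs. The true correlation is not in the protocol. No stated figure changes, and the sample size is unaffected because it was not derived from a hypothesis. The change is worth making because it is cheap and answers the stated objective directly.

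**What to change.** Add a paragraph to 8.2 along these lines:

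*Baseline peak-to-peak noise is analysed as the within-subject difference, Cube minus commercial system (or the log ratio), over matched channels and time windows, separately for bipolar and unipolar recordings. Differences are averaged to one value per subject for each recording type. The subject-level values are summarised descriptively, and their mean is reported with a 95% confidence interval, where n is the number of subjects with paired recordings. The number of subjects without a usable pair is also reported.*

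Keep the per-system summaries as supporting tables. If a statistical analysis plan holds the matching rules and computational detail, 8.2 can refer to it, but the contrast and the unit should stand in the protocol.

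The cost is one paragraph, the matching of recordings that the post-procedure comparison in 5.3.4 already implies, and a little programming. It needs no further patients, procedures or hypothesis test. Precision may look less favourable than a channel-level count would suggest, because n can be no larger than the number of subjects with both recordings.

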#### 4.4.1. Inclusion Criteria

Eligible subjects will meet all of the following inclusion criteria:

1. Subject indicated by investigator for catheter ablation or diagnostic electrophysiology procedure.
2. Male or non-pregnant female aged  $\geq 18$  years. Female subjects of childbearing potential must have a negative pregnancy test (per site standard test) within 7 days prior to index procedure.
3. Able and willing to directly provide informed consent.

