### **5.3.3. Screen Failures**

Subjects not meeting all study entry criteria will be designated as screen failures. End of study procedures will not be performed for these subjects, but their reason for ineligibility will be recorded on the Screening Log. Screen failures are counted towards the total study enrollment.

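### Does the missing-data rule in section 8.2 let lost recordings drop out of the technical success rate?

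*Protocol*

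**What the plan says.** Protocol section 5.1 defines the primary performance endpoint as "technical success of CathVision Cube® System to collect and record intracardiac signals during EP procedures" and lists four points of focus. One is "Logging time for arrhythmia termination / block"; another, baseline noise, is continuous. The section gives no success threshold, no denominator and no rule for a subject whose recording is absent.

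Section 8.2 sets one descriptive rule for all variables. Categorical data are shown as "number of non-missing observations and percentages by categories". It adds "Number and percent of missing data, if any, will also be summarized", and then "Missing data will not be replaced or imputed". No endpoint is exempted.

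Three other sections bear on the point:
- Section 4.4.1 admits both treatment and diagnostic cases: "Subject indicated by investigator for catheter ablation or diagnostic electrophysiology procedure".
- Section 5.3.3 says "Screen failures are counted towards the total study enrollment", so fewer than 30 subjects may reach the index procedure.
- Section 7.7 assigns a Device Deficiency CRF to "all device deficiencies, or malfunctions that occur during the course of the study, whether or not they were associated with an adverse event". Its list includes power, saving, retrieval, backup and recording faults of the Cube.

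**The concern.** For most endpoints, leaving missing values alone is a harmless convention. Here the absence of data may be the event being measured. If the Cube fails to power on, crashes or cannot save, there may be no file, and an analyst applying section 8.2 mechanically could treat that subject as missing. The subject would then leave both numerator and denominator, and the success percentage could only rise. The study is descriptive, so that percentage may be what readers take away.

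Two smaller doubts go with it:
- A blank for termination or block could mean that no such event occurred, which is likely in a diagnostic procedure, or that the device missed it.
- Sections 5.3.1 and 5.3.4 list device malfunctions at the index procedure but not at discharge. Section 5.3.4 places the comparison of the two systems' data after the procedure, when a retrieval or backup fault might first appear.

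**Working it through.** **Inputs.** The maximum enrolment is 30 (synopsis; section 4.4). Section 8.1 applies no hypothesis, and the protocol gives no success rate or threshold, so there is no planned figure to reproduce. The number of lost recordings, k, is not given; I assume 1 to 5. Because screen failures use up enrolment places, I also assume N = 25 connected subjects. Every subject with a recording is taken as a success.

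**Formulas.** If losses are dropped, success = (N − k)/(N − k) = 100%. If losses count as failures, success = (N − k)/N. The gap is k/N. Intervals are exact (Clopper-Pearson) 95% limits; section 8.2 does not plan them, and they are shown only for scale.

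| N | k | Dropped | Counted as failure | Gap (points) |
|---|---|---|---|---|
| 30 | 1 | 29/29 = 100% (88.1 to 100) | 29/30 = 96.7% (82.8 to 99.9) | 3.3 |
| 30 | 3 | 27/27 = 100% (87.2 to 100) | 27/30 = 90.0% (73.5 to 97.9) | 10.0 |
| 30 | 5 | 25/25 = 100% (86.3 to 100) | 25/30 = 83.3% (65.3 to 94.4) | 16.7 |
| 25 | 1 | 24/24 = 100% (85.8 to 100) | 24/25 = 96.0% (79.6 to 99.9) | 4.0 |
| 25 | 3 | 22/22 = 100% (84.6 to 100) | 22/25 = 88.0% (68.8 to 97.5) | 12.0 |
| 25 | 5 | 20/20 = 100% (83.2 to 100) | 20/25 = 80.0% (59.3 to 93.2) | 20.0 |

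The arithmetic is sound. The question is whether the protocol leads to the third column.

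**Step 1: is a failed recording missing data?** The third column requires it to be coded so, and no section says that. The endpoint is success in recording. If the Cube was connected and did not record, the outcome is known: failure. Entering a known outcome replaces nothing, so the sentence against imputation does not apply and no exemption from it is needed.

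**Step 2: are percentages taken on non-missing subjects only?** Section 8.2 reports a non-missing count and percentages but does not name the divisor. That divisor is the natural reading, not a stated rule. The percentage missing, in turn, needs the total as its base.

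**Step 3: what if both steps were taken anyway?** With N = 30 and k = 3, the table would show 27/27 beside 3 missing, 3/30 = 10%. A reader can recover 27/30 from that, and the three faults would also appear on Device Deficiency CRFs.

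**Smaller doubts.** Section 5.1 names termination or block as a point of focus and does not say that every subject must yield a time, so a not-applicable code is ordinary CRF detail. The schedule in section 5.3.1 shows when malfunctions are routinely asked about. Section 7.7 is driven by the event, has no visit limit and already covers faults found later; the grid does not cancel it.

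**The case for a change.** The strongest case for a change is that the protocol is not merely silent: it states a blanket rule. A SAP that turned blanks into failures could look at odds with it. The faults that would cause blanks are ones section 7.7 itself anticipates. Sponsor personnel operate the device and help collect its technical data (sections 3 and 9.5), which is a reason to fix the coding in advance. Dropping losses caused by the device can never lower the success rate, and one sentence would settle the matter at almost no cost.

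Part of this stands. Neither section 5.1 nor section 8.2 names the denominator or says that a recording lost through the device is a failure, and a clarifying sentence would do no harm. The supposed conflict with a SAP does not stand, because recording an observed failure is not imputation. Section 9.5 also requires the investigator to verify and countersign data collected by the sponsor's designee.

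The obvious remedy has a fault of its own. Counting every absent recording after attempted connection as a failure would charge the Cube with losses it did not cause, such as a catheter fault (listed in section 7.7) or a withdrawal (section 5.4.2). That would bias the rate the other way.

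**Conclusion.** No change is needed. This is an ambiguity that an analyst would resolve sensibly: among subjects in whom recording was attempted, a recording lost through the device is a failure and stays in the denominator; losses for other reasons are listed separately; noise summaries state how many subjects had no recording. These are coding and denominator definitions of the kind usually given in a SAP or CRF, and the SAP is not at hand.

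Read at its worst, section 8.2 could raise the reported rate by 3.3 to 16.7 points with 30 connected subjects, or by 4.0 to 20.0 points with 25. Those figures rest on assumed losses of 1 to 5 and on two steps the protocol does not state. With no losses, both readings give 30/30. No pass or fail decision depends on the percentage, and the losses would remain visible in the missing-data counts and the device deficiency reports.
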